
 
• To conduct active detection of symptomatic and asymptomatic SARS-CoV-2 infection
 
	
 
• Laboratory-confirmed asymptomatic or symptomatic SARS-CoV-2 infection will be defined in participants: 
 
– Negative SARS-CoV-2 anti-nucleocapsid antibody blood test at Day 1 that becomes positive at Day 29 or later, OR
 
– Positive SARS-CoV-2 reverse transcriptase polymerase chain reaction (RT-PCR) from nasopharyngeal swab
 
 
 

 
• To assess the genetic and/or phenotypic relationships of isolated SARS-CoV-2 strains to the vaccine sequence
 
	
 
• Comparison of the SARS-CoV-2 genetic sequence of viral isolates with the vaccine sequence and characterization of immune responses to vaccine breakthrough isolates
 

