**Table 1-2: Part B Treatment Groups:**

Treatment Group	Vaccine	Dose Level 	N
1	mRNA-1283.529	CCI	70
2		CCI	70

Participants in both parts will have up to 7 study visits; 6 visits if screening and randomization/enrollment are performed on the same day. Study vaccine will be administered as a single dose on Day 1. Additional safety and immunogenicity study visits will occur on Days 8 (safety call only), 15, 29, 91, 181, and 366 (end of study [EoS]). Study visits will include scheduled safety phone calls every 2 weeks to collect MAAEs, AESIs, AEs leading to withdrawal, SAEs, and information about concomitant medications associated with these events, as well as to collect information about receipt of non-study vaccinations temporally associated with these events.

At the vaccination visit (Day 1), participants will be instructed how to document and report solicited ARs in a provided electronic diary. Solicited ARs will be assessed for 7 days after the injection (the day of injection and the following 6 days), and unsolicited AEs will be assessed for 28 days after each injection. Medically attended AEs, SAEs, AESIs, and AEs leading to withdrawal will be assessed throughout the study. All participants will be tested for the presence of SARS-CoV-2 anti-nucleocapsid antibodies at Days 1, 29, 91, 181, and 366, as well as by nasopharyngeal swab RT-PCR on Days 1, 29, 91, 181, and 366. Active surveillance for intercurrent or breakthrough SARS-CoV-2 infection will occur throughout the study and be reported as AEs (confirmed symptomatic infections will be reported as MAAEs if not an SAE). Symptomatic infection will be prompted by signs and symptoms meeting the US Centers for Disease Control and Prevention (CDC) case definition and the case definition from the Phase 3 study (mRNA-1273-P301) for coronavirus disease 2019 (COVID-19), as well as the clinical suspicion of the site investigator. Participants will be asked to contact the study site to arrange for a prompt, thorough, and careful assessment. Participants will have blood sampled at scheduled study site visits (Days 1, 15, 29, 91, 181, and 366) during the study for immunogenicity assessments or other medical concerns according to the investigator's judgment.

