### 6.6.1. Endpoint Definition/Derivation

#### 6.6.1.1. Derivation of SARS-CoV-2 Infection

SARS-CoV-2 infection is considered as either positive status of COVID-19 or asymptomatic SAS-CoV-2 infection for participants with negative pre-booster SARS-CoV-

2 status. It will be counted starting 14 days after the dose of IP SARS-CoV-2 infection will be defined in participants with negative pre-booster SARS-CoV-2 status by either:

- bAb levels against SARS-CoV-2 nucleocapsid protein negative at Day 1 that becomes positive after the IP injection, OR
- Positive RT-PCR after the dose of IP.

The date of documented infection will be the earlier of:

- Date of positive post-baseline RT-PCR result, or
- Date of positive post-baseline serology test result

The time to the first SARS-CoV-2 infection will be calculated as:

Time to the first SARS-CoV-2 infection = Date of the first documented infection – Date of the IP injection + 1.

Cases will be counted starting 14 days after the IP injection. They will be summarized by treatment group.

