#### **6.6.1.2. Derivation of Asymptomatic SARS-CoV-2 Infection**

The incidence of asymptomatic SARS-CoV-2 infection measured by RT-PCR of nasopharyngeal swabs and/or serology tests obtained at post-baseline visits is counted starting 14 days after the IP injection in participants with negative pre-booster SARS-CoV-2 status.

Asymptomatic SARS-CoV-2 infection is identified by absence of symptoms with positive status per RT-PCR or serology tests at a post-baseline visit, specifically:

- Absent of COVID-19 symptoms AND at least one from below:
- bAb levels against SARS-CoV-2 nucleocapsid protein negative at Day 1 that becomes positive after the IP injection, OR
- Positive RT-PCR test after the IP injection.

The date of the asymptomatic infection is the earlier date of positive serology test result based on bAb specific to SARS-CoV-2 nucleocapsid, or positive post-baseline RT-PCR, with absence of symptoms.

The time to the asymptomatic SARS-CoV-2 infection will be calculated as:

Time to the asymptomatic SARS-CoV-2 infection = Date of the asymptomatic SARS-CoV-2 infection – Date of the IP injection + 1.

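### The 14-day start for counting infections cannot act on seroconversions first seen at the Day 29 visit, because a serology-only case is dated by its sample

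*SAP*

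**What the plan says.** SAP Section 6.6.1.1 ends with the counting rule: "Cases will be counted starting 14 days after the IP injection. They will be summarized by treatment group". Section 6.6.1.2 says that asymptomatic infection "is counted starting 14 days after the IP injection in participants with negative pre-booster SARS-CoV-2 status".

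The serologic criterion, worded alike in both sections, is "bAb levels against SARS-CoV-2 nucleocapsid protein negative at Day 1 that becomes positive after the IP injection, OR" a positive RT-PCR. It sets no condition on when the infection was acquired.

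On dating, Section 6.6.1.1 states "The date of documented infection will be the earlier of" two dates: that of the positive post-baseline RT-PCR and the "Date of positive post-baseline serology test result". Section 6.6.1.2 dates asymptomatic cases in the same way. Time to infection is computed from this date in both sections.

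On the sampling schedule, SAP Section 4.1 has participants "tested for the presence of SARS-CoV-2 anti-nucleocapsid antibodies at Days 1, 29, 91, 181, and 366". Protocol Table 8 agrees that nothing is scheduled between Day 1 and Day 29: the Day 15 visit draws blood for humoral immunogenicity but not for anti-nucleocapsid serology. The Day 29 visit window is -7 to +3 days. An anti-nucleocapsid sample can come sooner only at an unscheduled visit.

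The endpoint itself is defined in Protocol Table 1 as "Negative SARS-CoV-2 anti-nucleocapsid antibody blood test at Day 1 that becomes positive at Day 29 or later, OR" a positive RT-PCR. SAP Section 3.1.3 repeats this.

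**The concern.** A counting rule based on time since injection works only if the date attached to a case says something about when the infection happened. For a serology-only case it does not. Protocol Section 7.3.6 itself describes the serologic assay as picking up resolved infections from the interval between visits. A first positive at Day 29 therefore places the infection somewhere between about Day 1 and Day 29, and possibly just before Day 1 if the participant was incubating with negative baseline tests.

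Two things follow. First, tables presented as cases from 14 days onward will contain cases that cannot be assigned to that period. At the Day 29 data cut, every serology-only case from a scheduled draw is of this kind. Second, whether an early infection counts depends on how it was found. One confirmed by an illness-visit swab on Day 5 is dated Day 5 and dropped, whereas a silent one acquired on the same day and found at the Day 29 draw is counted. The time-to-infection values for such cases, 22 to 32 days under the SAP formula, are times to detection.

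**Working it through.** The plan gives no figure on this point, so there is none to reproduce.

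**Step 1: does the rule ever exclude a Day 29 serology-only case?** The visit window is study Days 22 to 32, which is 21 to 31 days after injection. All of these are at least 14, so a serology-only case first seen at a scheduled Day 29 visit always passes. This step uses document figures only.

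**Step 2: what share of serology-detectable infections comes from the excluded period?** Let v be days from injection to the sample (28 at target, 21 and 31 at the window limits) and L the lag in days from infection to anti-nucleocapsid positivity. L and the incidence pattern are not in the documents, so both are assumptions. Infections acquired from day 0 to day v - L are positive at v. Under constant incidence:

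share = min(14, v - L) / (v - L)

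| Sample | L = 0 | L = 7 | L = 10 | L = 14 |
|---|---|---|---|---|
| Day 22 (v = 21) | 14/21 = 67% | 14/14 = 100% | 100% | 100% |
| Day 29 (v = 28) | 14/28 = 50% | 14/21 = 67% | 14/18 = 78% | 14/14 = 100% |
| Day 32 (v = 31) | 14/31 = 45% | 14/24 = 58% | 14/21 = 67% | 14/17 = 82% |

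**Step 3: incidence that changes over time.** If incidence doubles every d days, the share is (2^(14/d) - 1) / (2^((v - L)/d) - 1). At v = 28 and L = 7:

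- d = 28: 0.414/0.682 = 61%
- d = 14: 1/1.828 = 55%
- d = 7: 3/7 = 43%
- halving every 14 days: 0.5/0.646 = 77%

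With d = 7 and L = 10 the share is 3/4.94 = 61%.

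**Step 4: early cases already removed by RT-PCR.** Suppose a fraction f of infections from the excluded period was dated by an early swab and dropped, while all later ones stay. At v = 28 with constant incidence, share = 14(1 - f) / [14(1 - f) + (14 - L)]. With f = 0.5 this is 7/(7 + 7) = 50% at L = 7 and 7/(7 + 4) = 64% at L = 10.

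**Step 5: factors that raise the share.** If infections incubating at injection are included, the share at v = 28 is (14 + L)/28, which is 75% at L = 7 and 86% at L = 10. If the case must also be RT-PCR negative at the Day 29 swab, and swab positivity lasts P days (again an assumption), the share is 14/(28 - max(L, P)). At L = 7 this gives 67%, 78% and 100% for P = 7, 10 and 14.

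**The case against.** The strongest reply is that the SAP speaks of a date of *documented* infection, and dating by detection is consistent with that label. The documents never say what the 14-day start is for. That is fair, and the point here does not rest on a presumed purpose. It rests on a stated rule that cannot act on one class of cases.

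A reader might go further and infer that most of the Day 29 seroconversions counted were acquired in the excluded period. The documents do not support that. It needs a lag and an incidence pattern that they do not give, and Steps 2 to 4 show plausible settings at or below half. The shares in Step 2 also describe all serology-detectable infections, not only those left after early swab-dated cases are dropped.

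The swab-versus-serology contrast has limits too. No swab is scheduled between Day 1 and Day 29, and Protocol Section 7.3.6 leaves swabbing in the first 7 days largely to the investigator's judgment. The contrast is therefore mainly between symptomatic and silent infections. A silent infection found by the scheduled Day 29 swab is also dated by its sample.

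Finally, the consequence is modest. Protocol Section 8.5.2 plans no pre-specified efficacy analysis, no hypotheses are tested, and SAP Section 6.6.2 asks for counts and percentages on the FAS. The arms share one visit schedule, and no bias towards any arm is shown. The randomized comparison in Part A would at most be diluted. Part B arms are enrolled sequentially (Protocol Section 5.2), so their early periods fall at different calendar times and balance cannot be assumed there. None of this removes the labelling problem.

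**Conclusion.** The structural point holds on document facts alone: the 14-day rule cannot exclude a serology-only case first seen at a scheduled Day 29 visit, and early infections are counted or not according to how they were detected.

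The size is conditional. With constant incidence and a sample 28 days after injection, between half (zero lag) and all (lag of 14 days or more) of serology-detectable infections would come from the excluded period. The share drops below half with fast-rising incidence, with a late visit and little lag, or when many early cases were already dated by RT-PCR.

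Two stronger readings should be avoided. One is that the documents show a majority of these cases to be early. The other is that the issue reaches the primary immunogenicity results: those use PPIS-Neg, which is defined by status on or before the booster, and the optional sensitivity subset in SAP Section 6.4.2 looks at infection evidence through Day 29 or Day 91 without using the 14-day rule. The change is worth making because it is cheap and makes a reported count mean what its label says, but it concerns an exploratory, descriptive summary only.

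**What to change.** In SAP Sections 6.6.1.1 and 6.6.1.2, keep the endpoint definition (anti-nucleocapsid negative at Day 1, positive at Day 29 or later) and leave RT-PCR dating unchanged. Add a flag based on the last negative anti-nucleocapsid sample, and split serology-only cases in the summaries by treatment group:

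- **(a)** Last negative sample at least 14 days after injection: counted as post-14-day cases.
- **(b)** Last negative sample less than 14 days after injection: shown in a separate row labelled *onset before or after 14 days not determinable*. This row takes in participants who missed the Day 29 draw and were first positive later, so that no case is lost.

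Show the infection total with and without row (b). Section 7 of the SAP, which lists changes from the protocol, need not change on this account, since the endpoint stays as defined.

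The cost is one extra derivation from data already collected, and a smaller count of confirmed post-14-day cases. At the Day 29 cut nearly all serology-only cases will sit in row (b); the exceptions need a negative unscheduled sample at 14 days or later. Row (a) is still an approximation. A negative sample at v days rules out acquisition before day 14 only if L is at most v - 14, which is 7 days for a Day 22 visit, 14 for Day 29 and 17 for Day 32. A table footnote can say so.

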#### **6.6.1.2. Derivation of Asymptomatic SARS-CoV-2 Infection**

The incidence of asymptomatic SARS-CoV-2 infection measured by RT-PCR of nasopharyngeal swabs and/or serology tests obtained at post-baseline visits is counted starting 14 days after the IP injection in participants with negative pre-booster SARS-CoV-2 status.

Asymptomatic SARS-CoV-2 infection is identified by absence of symptoms with positive status per RT-PCR or serology tests at a post-baseline visit, specifically:

- Absent of COVID-19 symptoms AND at least one from below:
- bAb levels against SARS-CoV-2 nucleocapsid protein negative at Day 1 that becomes positive after the IP injection, OR
- Positive RT-PCR test after the IP injection.

The date of the asymptomatic infection is the earlier date of positive serology test result based on bAb specific to SARS-CoV-2 nucleocapsid, or positive post-baseline RT-PCR, with absence of symptoms.

The time to the asymptomatic SARS-CoV-2 infection will be calculated as:

Time to the asymptomatic SARS-CoV-2 infection = Date of the asymptomatic SARS-CoV-2 infection – Date of the IP injection + 1.

#### 6.6.1.3. Derivation of COVID-19

The incidence of the first occurrence of symptomatic COVID-19 infection cases is recorded starting 14 days after the injection. Surveillance for COVID-19 will be conducted through monthly contact and scheduled blood collection. Subjects reporting COVID-19 symptoms will be arranged an illness visit to collect an NP swab.

Two definitions of the COVID-19 will be evaluated:

1. Primary case definition per the Phase 3 study (mRNA-1273-P301): Cases are defined as participants meeting clinical criteria based on both symptoms for the COVID-19 and positive RT-PCR test results as described in [Table 2-1](#).
2. Secondary case definition based on CDC criteria: The presence of one of the CDC-listed symptoms ([Table 2-2](#)) and a positive RT-PCR test on a respiratory sample.

**Table 2-1. Derivation of primary case definition of COVID-19**

COVID-19 (per the Phase 3 study (mRNA-1273-P301))	
Post-baseline RT-PCR results	Positive, AND
Systemic Symptoms	at least TWO of the following systemic symptoms : Fever ( $\geq 38^{\circ}\text{C}$ ), chills, myalgia, headache, sore throat, new olfactory and taste disorder(s); OR
Respiratory Symptoms	at least ONE of the following respiratory signs/symptoms : cough, shortness of breath or difficulty breathing, OR clinical or radiographical evidence of pneumonia.

**Table 2-2. Derivation of secondary case definition of COVID-19**

COVID-19 (CDC criteria)	
Post-baseline RT-PCR results	Positive, AND
Systemic and Respiratory Symptoms	at least ONE of the following systemic or respiratory symptoms : Fever ( $\geq 38^{\circ}\text{C}$ ) or chills, cough, shortness of breath or difficulty breathing, fatigue, muscle or body aches (not

	related to exercise), headache, new loss of taste or smell, sore throat, congestion or runny nose, nausea or vomiting, diarrhea.
--	--

The date of documented COVID-19 will be the later date of the following two dates (date of positive RT-PCR test, and the date of eligible symptom(s)), and the two dates should be within 14 days of each other.

The time to the first occurrence of COVID-19 will be calculated as:

Time to the first occurrence of COVID-19 = Date of documented COVID-19 – Date of the IP injection + 1.

Cases will be counted starting 14 days after the IP injection.

#### **6.6.2. Analysis Method**

The number and percentage of subjects who had each type of event (i.e., an asymptomatic or a symptomatic SARS-CoV-2 infection) will be summarized with FAS.

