### **6.2. Participant Discontinuation/Withdrawal from the Study**

Participants who withdraw or are withdrawn from the study will not be replaced.

Participants can withdraw consent and withdraw from the study at any time, for any reason, without prejudice to further treatment the participant may need to receive. The investigator will request that the participant complete all study procedures pending at the time of withdrawal.

If a participant desires to withdraw from the study because of an AE, the investigator will attempt to obtain agreement to follow up with the participant until the event is considered resolved or stable and will then complete the EoS eCRF.

Information related to the withdrawal will be documented in the eCRF. The investigator will document whether the decision to withdraw a participant from the study was made by the participant or by the investigator, as well as which of the following possible reasons was responsible for withdrawal:

- AE (specify)
- AESI (specify)

- SAE (specify)
- Death
- Lost to follow-up (LTFU)
- Physician decision (specify)
- Pregnancy
- Protocol deviation
- Study terminated by Sponsor
- Withdrawal of consent by participant (specify)
- Other (specify)

Participants who are withdrawn from the study because of AEs (including SAEs and AESIs) must be clearly distinguished from participants who are withdrawn for other reasons.

Investigators will follow up with participants who are withdrawn from the study as a result of an SAE or AE until resolution of the event.

A participant withdrawing from the study may request destruction of any samples taken and not tested, and the investigator must document this in the site study records.

If the participant withdraws consent for disclosure of future information, the Sponsor may retain and continue to use any data collected before such a withdrawal of consent.

The Sponsor will continue to retain and use all research results that have already been collected for the study evaluation, unless the participant has requested destruction of these samples. All biological samples that have already been collected may be retained and analyzed at a later date (or as permitted by local regulations).

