### **5.3. Full Analysis Set (FAS)**

The FAS consists of all randomized/enrolled (Part A: randomized, Part B: enrolled) participants who receive one dose of IP. Participants will be included in the treatment group to which they were randomized/enrolled.

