## 6. Statistical Analysis

### 6.1. General Considerations

Please refer to Table 8 in the protocol for Schedule of Events (SoE).

The following follow-up periods for safety analyses and Concomitant Medications will be used:

- Overall follow-up period (throughout the study): from the day of the IP injection (Day 1) to the earliest date of (study completion, discontinuation from the study, or death)
- Up to 28 days follow-up period: from the day of the IP injection (Day 1) to the earliest date of (the day of the IP injection and 27 subsequent days, discontinuation from the study, or death)
- After 28 days follow-up period: from the 28 days after the IP injection to the earliest date of (study completion, discontinuation from the study, or death)
- 7-day follow-up period: from the day of the IP injection (Day 1) to the earliest date of (Day 7 after the IP injection, discontinuation from the study, or death)

**Continuous variables** will be summarized using the following descriptive summary statistics: the number of subjects (n), mean, standard deviation (SD), median, minimum (min), and maximum (max).

**Categorical variables** will be summarized using counts and percentages.

**Baseline value**, unless specified otherwise, is defined as the most recent non-missing measurement (scheduled or unscheduled) collected before the dose of IP in this study.

For the summary statistics of all numerical variables unless otherwise specified, the display precision will follow programming standards. Please see [Appendix A](#) for variable display standards.

When count data are presented, the percentage will be suppressed when the count is zero in order to draw attention to the non-zero counts. A row denoted “Missing” will be included in count tabulations where specified on the shells to account for dropouts and missing values. The denominator for all percentages will be the number of subjects in the treatment group within the analysis set of interest, unless otherwise specified.

**End of Study** (EoS) for the participants is defined as any of completion of the study if the participant has completed all phases of the study including the last scheduled procedure as shown in the SoE (Table 8 in the protocol), discontinuation of study due to any reason, death, and termination of the trial by the Sponsor.

**Pre-booster SARS-CoV-2 status** is determined by using virologic and serologic evidence of SARS-CoV-2 infection on or before Day 1 (pre-booster).

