## **6.9. Final Analysis**

The final analysis of all endpoints will be performed after all participants (Part A and Part B) have completed all planned study procedures. Results of this analysis will be presented in a final CSR, including individual listings. The final CSR will include full analyses of all safety and immunogenicity data through Day 366 (Month 12).

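### SAP 6.6.2 summarises infection and COVID-19 only as percentages of everyone dosed, so participants who leave event-free count as non-cases and the final figures modestly understate Day 366 risk

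*SAP*

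**What the plan says.** SAP 6.6.2 is a single sentence. It promises "The number and percentage of subjects who had each type of event", asymptomatic or symptomatic, with the FAS as the analysis set. SAP 6.1 fixes the denominator: "The denominator for all percentages will be the number of subjects in the treatment group within the analysis set of interest, unless otherwise specified". SAP 6.6.2 specifies no other denominator. The FAS in SAP 5.3 is all randomised or enrolled "participants who receive one dose of IP", with no follow-up requirement. Protocol 6.2 adds: "Participants who withdraw or are withdrawn from the study will not be replaced". SAP 6.1 leaves missing data unimputed, apart from listed exceptions that do not cover these endpoints.

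SAP 6.6.1 derives more than 6.6.2 uses. Section 6.6.1.1 states "The time to the first SARS-CoV-2 infection will be calculated as" and gives a formula. Section 6.6.1.2 does the same for asymptomatic infection, and 6.6.1.3 states "The time to the first occurrence of COVID-19 will be calculated as". Cases count from 14 days after injection. Neither document contains an analysis of these times, a censoring rule for them, a Kaplan-Meier estimate or a rate per person-time. The final analysis (SAP 6.9) covers data through Day 366.

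**The concern.** A percentage of everyone dosed equals the risk to Day 366 only if everyone is followed to Day 366. A participant who withdraws or is lost, even before case counting starts, stays in the denominator as event-free. Any infection after the last contact is unseen, and later serology can recover it only in participants who return. The direction of the error is therefore known: the percentage is too low. Its size depends on how many leave an arm and when, so two arms with equal risk and unequal dropout would show different percentages.

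This is the only summary specified for the exploratory infection objective in either part. The derived times to event suggest that a follow-up-adjusted analysis was intended but not written, or that the derivations are left over.

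**Working it through.** **Inputs.** From the documents: up to 70 participants per arm (SAP 4.2), counting from 14 days after injection (SAP 6.6.1), and the last visit 365 days after injection with a window of ±14 days (Protocol Table 8). The plan has no figure to reproduce. The risk R and the proportion d leaving by Day 366 are assumptions, varied below.

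**Expected percentage, events observed continuously.** Take a constant infection hazard h = −ln(1−R)/351, where 351 = 365 − 14, and a constant dropout hazard g = −ln(1−d)/365. The expected FAS proportion is exp(−14g) × h/(h+g) × [1 − exp(−351(h+g))].

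Example with R = 40% and d = 20%: h = 0.001455 and g = 0.000611, so 0.9915 × 0.7042 × 0.5159 = 0.360.

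| Assumed R | d = 5% | d = 10% | d = 20% | d = 30% |
|---|---|---|---|---|
| 20% | 19.5 | 19.0 | 17.9 | 16.8 |
| 30% | 29.3 | 28.5 | 26.9 | 25.3 |
| 40% | 39.0 | 38.0 | 36.0 | 33.9 |

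At R = 40% the relative shortfall is 2.4%, 4.9%, 10.0% and 15.3%, about half of d. If all leavers go at about Day 29, the expected figure is (1−d)R + d[1 − exp(−15h)]. For R = 20% that gives 19.0, 18.1, 16.2 and 14.3, which is close to the full dropout rate in relative terms.

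**False gap between two arms of equal risk, 5% versus 20% dropout.** The half-width is 1.96 × √(2R(1−R)/70).

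| Assumed R | Gap, spread dropout | Gap, all leave at Day 29 | 95% half-width of a difference |
|---|---|---|---|
| 10% | 0.8 | 1.4 | 9.9 |
| 20% | 1.6 | 2.9 | 13.3 |
| 30% | 2.3 | 4.3 | 15.2 |
| 40% | 3.0 | 5.7 | 16.2 |

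A 15-point dropout difference is 0.15 × 70 = 10.5 participants. Three extra leavers (3.5/70 = 5% against 6.5/70 = 9.3%) at R = 40% give 39.0% against 38.2%. That is 0.8 points, or 0.008 × 70 ≈ 0.6 of a participant.

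**Day 29.** With the hazard for R = 20%, the risk over the first 14 counted days is 1 − exp(−14h) = 0.89%. If 2% leave before counting starts, it becomes 0.98 × 0.89% = 0.87%.

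**Do adjusted summaries work?** This depends on how the event is found.

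- *Continuously observed events* (simulation, 70 per arm, R = 20%, dropout 5%, 20%, 30%): the crude percentage is 19.6, 17.9, 16.9 and Kaplan-Meier is 20.1, 20.0, 20.1. The rate is 23.5, 23.4, 23.5 per 100 person-years, against a true −ln(0.8)/351 × 365.25 × 100 = 23.2.
- *Events found only at scheduled visits* (simulation, visits uniform within the Table 8 windows, infection dated at the positive test as in SAP 6.6.1.1): with no dropout, the rate is about 5%, 8% and 14% below the true hazard at R = 20%, 40% and 60%. Kaplan-Meier read at calendar Day 366 gives about 33% for a true 40%, because about half the last visits fall after that day. The crude percentage gives 40%. Kaplan-Meier on nominal visit times gives 40% with no dropout and with 20% dropout.

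**The case against.** The strongest reply is that the SAP never calls this percentage a 12-month risk. The objective is active detection of infection. Protocol 8.5.2 has no pre-specified efficacy analysis and says only that exploratory analyses may be done, and Protocol 8.2 tests no hypotheses. As a description of cases observed, the percentage is correct. The SAP also lets a reader see unequal follow-up: 6.2.1 tabulates discontinuation and reasons by arm, 6.2.5 summarises study duration since injection, and 6.1 allows a row for missing values where the table shells specify one. SAP 6.1 even defines an overall follow-up period, although for safety and concomitant medications.

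Most of this stands, and it limits the size of the point. It does not remove the mechanism. A row for missing values leaves the denominator unchanged. Study duration is not time at risk, which starts 14 days after injection and stops at the first event. The derived times to event still have no use.

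A reader might infer that a few extra early withdrawals would make an arm look protected. The arithmetic does not support that: three extra leavers in 70 move the figure by less than one participant. A reader might also infer that a person-time rate and a Kaplan-Meier estimate at Day 366 would correct every endpoint. They do so for continuously observed events. For visit-detected infection, the first is biased low and the second can be worse than the crude percentage.

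**Conclusion.** The point holds as a minor one. At the final analysis the FAS percentage understates Day 366 risk whenever participants leave event-free, and arms with different dropout are not strictly comparable. Under constant hazards the relative understatement is roughly half the dropout rate when leaving is spread over the year, and nearer the whole rate when leaving is early. All risks and dropout rates used here are assumed, and the documents give no sign that dropout will differ by arm.

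The effect is negligible at the Part A primary analysis and the Part B interim analysis, both at Day 29. Even a 5% versus 20% dropout difference gives a gap well inside sampling error at 70 per arm. No stated power or hypothesis test is affected. The documents do not support reading SAP 6.6.2 as a claim about 12-month risk.

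A separate matter is that the infection derivations admit only participants negative before the booster, while the denominator is the whole FAS. Correcting that would not remove the dropout effect.

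**What to change.** In SAP 6.6.2:

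1. Keep the counts and percentages, label them as observed cases, and show person-time of follow-up by treatment group.
2. For symptomatic COVID-19 under both case definitions, add by treatment group the incidence rate per person-time with an exact Poisson 95% CI. Kaplan-Meier cumulative incidence is optional. Time at risk runs from 14 days after injection to the earliest of first event, discontinuation, death or end of study.
3. For endpoints found mainly at scheduled swab or serology visits, do not use a Kaplan-Meier estimate cut at calendar Day 366 or an unadjusted rate dated at the positive test. Use a life-table estimate on nominal visits, or an interval-censored estimate, through the Month 12 visit.
4. Apply one censoring rule to cases and non-cases alike. Counting illness-visit cases after the last scheduled visit, while censoring non-cases at that visit, would inflate the estimate. Treat symptomatic COVID-19 as a competing event for asymptomatic infection.

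The cost is SAP wording and one extra exploratory table per endpoint. The event, visit and disposition dates are already collected, so no new data or participants are needed. The added estimates assume non-informative dropout, which should be stated beside them.
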